4. SUBJECT POPULATION

Screening for eligible subjects will be performed as soon as possible following admission to the ER or hospitalization, such that subjects are randomized within 5 days of RSV symptom onset. Special attention will be paid to determine the duration of RSV symptoms from onset till time of randomization as accurately as possible. Male or female infants and children ≥ 28 days to ≤ 36 months of age diagnosed with RSV infection based on a PCR-based diagnostic assay (with or without coinfection with another respiratory pathogen) who have been (or will be) admitted to the hospital and whose parents have signed informed consent will be enrolled. Subjects who were admitted to the hospital for another reason but develop an acute respiratory illness while being hospitalized are also eligible for screening.

The inclusion and exclusion criteria for enrolling subjects in this study are described in the following 2 subsections. If there is a question about the inclusion or exclusion criteria below, the investigator must consult with the appropriate sponsor representative and resolve any issues before enrolling a subject in the study. Waivers are not allowed.

For a discussion of the statistical considerations of subject selection, refer to Section 11.2, Sample Size Determination.

4.1. Inclusion Criteria

Each potential subject must satisfy all of the following criteria to be enrolled in the study:

1. Male or female infants and children ≥ 28 days to ≤ 36 months of age, defined at the time of randomization.
2. Subjects hospitalized (or in ER) at the time of randomization and unlikely to be discharged for the first 24 hours after randomization.
3. Subjects diagnosed with RSV infection using a PCR-based molecular diagnostic assay, with or without coinfection with another respiratory pathogen (respiratory virus or bacteria).

NOTE: In cases where commercial PCR-based assays are not available at the site, the sponsor should be consulted for agreement on the assay to be used.

4. Subjects who have an acute respiratory illness with signs and symptoms consistent with a viral infection (eg, fever, cough, nasal congestion, runny nose, sore throat, myalgia, lethargy, shortness of breath, or wheezing) with onset ≤ 5 days from the anticipated time of randomization. Onset of symptoms is defined as the first time (within 1 hour) the parent(s)/caregiver(s) becomes aware of respiratory or systemic symptoms of RSV infection.
5. With the exception of the symptoms related to the RSV infection or defined comorbid condition for severe RSV disease (prematurity at birth [subject's gestational age was < 37 weeks; for infants < 1 year old at randomization], bronchopulmonary dysplasia,

congenital heart disease, other congenital diseases, Down syndrome, neuromuscular impairment, or cystic fibrosis), subjects must be medically stable on the basis of physical examination, medical history, vital signs/SpO₂, and ECG performed at screening. If there are abnormalities, they must be consistent with the underlying condition in the study population and/or the RSV infection. This determination must be recorded in the subject's source documents and initialed by the investigator. Subjects with comorbidities will be allowed to be enrolled once the IDMC has reviewed the PK and safety data of the highest dose that will be used in this study and once the IDMC has recommended opening recruitment to this group. Sites will be notified when the restriction is lifted.

6. Subjects must be medically stable on the basis of clinical laboratory tests performed at screening. If the results of the serum chemistry panel or hematology are outside the normal reference ranges, the subject may be included only if the investigator judges the abnormalities or deviations from normal do not pose an unacceptable risk to the subject, are not clinically significant, or are appropriate and reasonable for the population under study, and have no specific cutoff per the exclusion criteria. This determination must be recorded in the subject's source documents and initialed by the investigator. A single repeat laboratory evaluation is allowed for eligibility determination.
7. The subject's estimated glomerular filtration rate (eGFR) is not below the lower limit of normal for the subject's age (Schwartz equation calculation see [Attachment 3](#)).
8. In the investigator's opinion, the subject's legally acceptable representative understands and is able to comply with protocol requirements, instructions, and protocol-stated restrictions, and the subject is likely to complete the study as planned.
9. The subject's legally acceptable representative must sign an informed consent form (ICF) indicating that he or she understands the purpose of, and procedures required for, the study and is willing for the subject to participate in the study.

4.2. Exclusion Criteria

Any potential subject who meets any of the following criteria will be excluded from participating in the study:

1. Subjects who are not expected to survive for more than 48 hours.
2. Subjects who have had major thoracic or abdominal surgery in the 6 weeks prior to randomization.

3. Subjects who received (within 12 months prior to screening) or who are currently on a waiting list for a bone marrow, stem cell, or solid organ transplant, who received radiation or chemotherapy (within 12 months prior to screening), or who are currently taking immunosuppressive medication (refer to Section 8, Pre-study and Concomitant Therapy).
4. Subjects who have a known or suspected immunodeficiency (except immunoglobulin A [IgA] deficiency), such as a known human immunodeficiency virus infection.
5. Subjects who have a history of or concurrent illness (beyond a defined comorbid condition for severe RSV disease) that in the opinion of the investigator, might confound the results of the study or pose an additional risk in administering study drug to the subject, or that could prevent, limit, or confound the protocol-specified assessments such as liver or renal insufficiency; significant cardiac, vascular, pulmonary, gastrointestinal, endocrine, neurologic, hematologic, rheumatologic, metabolic disturbances, or genetic diseases that result in immunosuppression. These may include, but are not limited to bacteremia, organ dysfunction, or other severe comorbidities.
6. Subjects who have a poorly functioning gastrointestinal tract (ie, unable to absorb drugs or nutrition via enteral route).

NOTE: The use of IV fluids is not exclusionary so long as the investigator believes the subject's gastrointestinal tract still functions properly (ie, is able to absorb drugs or nutrition).
7. Subjects being treated with extracorporeal membrane oxygenation.
8. Subject receiving chronic oxygen therapy at home prior to admission.
9. Subjects who have taken any disallowed therapies as noted in Section 8, Prestudy and Concomitant Therapy, before the planned first dose of study drug.
10. Subjects who received prescription medications intended to prevent or treat the RSV infection itself (eg, ribavirin, IV immunoglobulin, palivizumab), an investigational drug, an investigational vaccine, or used an invasive investigational medical device within 30 days or 5 half-lives (whichever is longer) before the planned first dose of study drug, or is currently enrolled in an investigational study.
11. Subjects who have known allergies, hypersensitivity, or intolerance to lumicitabine or its excipients (refer to Investigator's Brochure).¹⁶
12. Subjects legally acceptable representative unwilling to have subject undergo mid-turbinate nasal swab procedures or subjects with any physical abnormality which limits the ability to collect nasal swabs.

13. Subjects who are being breastfed by a mother taking any of the excluded medications as noted in Section 8, Prestudy and Concomitant Therapy.
14. Subject's legally acceptable representative ie, parent(s)/legal guardian/caregiver(s), is not able to communicate reliably with the investigator.
15. Subjects with any condition for which, in the opinion of the investigator, participation would not be in the best interest of the subject (eg, compromise the well-being) or that could prevent, limit, or confound the protocol-specified assessments.
16. Subjects aged ≥ 28 days to 35 days with < 8.0 g/dL (Grade 3) hemoglobin or a cardiac failure secondary to anemia (Grade 4) and subjects aged ≥ 36 days to 36 months with < 7.0 g/dL (Grade 3) hemoglobin or cardiac failure secondary to anemia (Grade 4).
17. Subjects aged ≥ 28 days to 60 days with $< 899/\text{mm}^3$ absolute neutrophil count) and subjects aged ≥ 61 days to ≤ 36 months with $< 399/\text{mm}^3$ absolute neutrophil count.
18. Subjects aged ≥ 28 days to ≤ 36 months with $< 49,999/\text{mm}^3$ platelet count (Grade 3/4).

NOTE: Investigators should ensure that all study enrollment criteria have been met at screening. If a subject's clinical status changes (including any available laboratory results or receipt of additional medical records) after screening but before the first dose of study drug is given such that he or she no longer meets all eligibility criteria, then the subject should be excluded from participation in the study. Section 9.1.2, Screening Phase, describes options for retesting. Section 17.4, Source Documentation, describes the required documentation to support meeting the enrollment criteria.

4.3. Prohibitions and Restrictions

Parent(s)/caregiver(s) must be willing and able to adhere to the following prohibitions and restrictions during the course of the study for the subject to be eligible for participation:

1. Refer to Section 8, Prestudy and Concomitant Therapy for details regarding prohibited and restricted therapy during the study.
2. Agree to follow all requirements that must be met during the study as noted in the Inclusion and Exclusion Criteria.
3. Concurrent administration of medications/use of licensed devices is allowed as supportive therapy per local standard of care, as long as the medication/licensed device will not affect the subject's participation in the study and is in accordance with allowed concomitant therapy. Parent(s)/caregiver(s) must agree to refrain from administering any new prescription or nonprescription medications other than study drug or those allowed as concomitant medications. If a disallowed medication is required it must be first discussed with investigational staff. Breastfeeding mothers also need to comply with the guidelines regarding concomitant medication.

5. TREATMENT ALLOCATION AND BLINDING

Treatment Allocation

Procedures for Randomization and Stratification

Central randomization will be implemented in this study. Subjects will be randomly assigned based on a computer-generated randomization schedule prepared before the start of the study by or under the supervision of the sponsor. The randomization will be balanced by using randomly permuted blocks and will be stratified by duration of RSV symptoms from onset till time of randomization (≤ 3 days versus > 3 to ≤ 5 days) and by presence or absence of comorbidity. The interactive web response system (IWRS) will assign a unique treatment code, which will dictate the treatment assignment and matching study drug kit for the subject. The requestor must use his or her own user identification and personal identification number when contacting the IWRS, and will then give the relevant subject details to uniquely identify the subject.

Blinding

The investigator will not be provided with randomization codes. The codes will be maintained within the IWRS, which has the functionality to allow the investigator to break the blind for an individual subject.

Data that may potentially unblind the treatment assignment (ie, study drug serum concentrations, study drug preparation/accountability data, treatment allocation, biomarker or other specific laboratory data) will be handled with special care to ensure that the integrity of the blind is maintained and the potential for bias is minimized. This can include making special provisions, such as segregating the data in question from view by the investigators, clinical team, or others as appropriate until the time of database lock and unblinding.

Under normal circumstances, the blind should not be broken until the unblinded IDMC review takes place (see Section 11.10, Data Monitoring Committee). The blind will be broken for the interim analyses (see Section 11.9, Interim Analysis) or when all subjects have completed the study and the database is finalized. Otherwise, the blind should be broken only if specific emergency treatment/course of action would be dictated by knowing the treatment status of the subject. In such cases, the investigator may in an emergency determine the identity of the treatment by contacting the IWRS. It is strongly recommended that the investigator contact the sponsor or its designee if possible to discuss the particular situation, before breaking the blind. Telephone contact with the sponsor or its designee will be available 24 hours per day, 7 days per week. In the event the blind is broken, the sponsor must be informed as soon as possible. The date, time, and reason for the unblinding must be documented by the IWRS, in the appropriate section of the electronic case report form (eCRF) and in the source document. The documentation received from the IWRS indicating the code break must be retained with the subject's source documents in a secure manner.

Subjects who have had their treatment assignment unblinded should continue to return for scheduled evaluations. Discontinuation of study treatment should be done only for the reasons

stated in Section 10.2, Discontinuation of Study Treatment/Withdrawal From the Study; unblinding of study treatment should not necessarily lead to study drug discontinuation.

In general, randomization codes will be disclosed fully only if the study is completed and the clinical database is closed. However, if an interim analysis is specified, the randomization codes and, if required, the translation of randomization codes into treatment and control groups will be disclosed to those authorized and only for those subjects included in the interim analysis.

In the event that the subject continues into the long-term follow-up study, then the subject and investigator will remain blinded until the follow-up study is completed.

6. DOSAGE AND ADMINISTRATION

The study drug will be provided as a powder for suspension for oral administration. Study drug administration should start as soon as possible, but no later than 4 hours after randomization in order to maximize the opportunity for the compound to inhibit viral replication and potentially improve outcomes.

Subjects will be dosed with a single LD followed by 9 MDs twice daily (minimum 8 hours and maximum 16 hours apart with no more than 2 doses per calendar day) during Day 1 to Day 5/6 (depending on the timing of the LD).

Administration of each dose should occur at approximately the same time each day and after the once-daily collection of the mid-turbinate nasal swab. Lumicitabine can be administered without regard to food. The date and time of dose administration, the date and time of food intake (limited to the food ingested within 30 minutes before or after study drug administration), and the type of food will be recorded in the eCRF for hospitalized subjects.

Lumicitabine and placebo will be supplied as a powder in amber glass bottles containing 1,891 mg lumicitabine or placebo with a child-resistant cap. The powder should be suspended with solvent prior to oral administration, providing a 60 mg/mL suspension, under the supervision of the investigator or a qualified member of the study-site personnel, or by a hospital/clinic pharmacist. Instructions for preparation of weight-based study formulations are provided in the pharmacy manual.

In case a dose is missed, the dose may be given up to 6 hours after the scheduled time. If more time has elapsed the dose should be skipped and the next dose should be given at the next scheduled timepoint per the initial dose schedule.

In case the subject is discharged prior to the completion of dosing, study drug administration will continued at home by the parent(s)/caregiver(s) until all doses are administered (Day 5/6). The investigator/study-site personnel will instruct parent(s)/caregiver(s) on how to store study drug for at-home use as indicated for this protocol (see pharmacy manual).

An overdose in this study is defined as a calculated dose exceeding the planned dose.

7. TREATMENT COMPLIANCE

Study drug will be administered orally or via nasogastric tube (if applicable) by designated study-site personnel at the study-site during hospitalization. The investigator/study-site personnel will maintain a log of all study drug administered. Drug supplies for each subject will be inventoried and accounted for.

In the event of the subject being discharged (after Day 2 procedures) from hospital during the dosing period, the parent(s)/caregiver(s) will administer study drug at home and will be required to document the dose of study drug in a study medication log on the electronic device provided during screening.

Parent(s)/caregiver(s) will receive instructions on compliance with study drug administration on the day of hospital discharge. During the course of the study, the investigator or designated study-site personnel will be responsible for providing additional instruction to re-educate any parent(s)/caregiver(s) who is not able to ensure compliance with the study drug.

In case of vomiting or regurgitation, the subject should not be redosed. If the subject vomits, regurgitates, or does not completely swallow the study drug, it should be recorded in the eCRF, source documents (during hospitalization) and in the electronic parent(s)/caregiver(s) eCOA device (post discharge).

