- RSV viral load AUC from immediately prior to first dose of study drug (baseline) until Day 10 and until Day 14.
- RSV viral load AUC in subjects assigned to a longer dosing duration, if dosing duration is increased by the IDMC, from baseline until 1 day (+2 days) after the last dose of study drug.
- Sequence changes (postbaseline) in the RSV polymerase L-gene and other regions (if warranted) of the RSV genome compared with baseline sequences.
- Acceptability and palatability of the lumicitabine formulation as assessed by the parent(s)/caregiver(s) eCOA.

Exploratory Endpoints

The exploratory endpoints of this study are:

- The duration and severity of signs and symptoms of RSV infection as assessed by the PRESORS questionnaire completed by the parent(s)/caregiver(s) in the eCOA device.
- Number of hours the subject's parent(s)/caregiver(s) missed from usual activities.
- Medical resource utilization.
- RSV infectious viral load as measured using a quantitative viral culture (plaque assay).
- RSV viral load as measured by qRT-PCR of mid-turbinate nasal swabs and endotracheal samples in intubated subjects.

Refer to Section 9, Study Evaluations, for evaluations related to endpoints.

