- Floppy/lethargic/poor interaction
- Only responds to pain/unresponsive

7. Signs of increased work of breathing now

7.1. Does the subject show any of these signs of increased work of breathing now? (note all that apply)

- Subcostal retractions
- Intercostal retractions
- Tracheosternal retractions
- Tachypnea [*tachypnea needs defined within the system WHO values pop-up?*]
- None of the above [*cannot be checked if any other options selected*]

7.2. Does the subject show any of these signs of increased work of breathing now? (note all that apply)

- Nasal flaring
- Head bobbing
- Grunting
- Other signs of increased work of breathing not already reported
- None of the above [*cannot be checked if any other options selected*]

8. Does the subject show any signs of cyanosis?

- Yes
- No

9. Describe the subject's coughing now (select one)

- Little or no coughing
- Occasional strong cough, sometimes productive
- Frequent cough, sometimes causing choking, gagging, or vomiting

10. Describe the subject's nasal secretions now (select one)

- None
- Minimal, easily cleared with suctioning
- Moderate, but could be cleared with suctioning
- Extensive, requires frequent suctioning

11. Describe the subject's wheezing now (select one)

- No wheezing
- Terminal expiratory wheezing or only with stethoscope
- Entire expiration or audible during expiration without stethoscope
- Inspiration and expiration without stethoscope

12. Does the subject appear to be dehydrated now?

- Yes
- No

13. Do you have any concerns relating to the subject's overall condition? (select one)

- No concerns (condition is stable or improving)
- Some concerns (may become unstable/requires close observation)
- Extremely concerned (unstable, requires immediate medical review)

14. Overall, how would you rate the subject's current health status? (select one)

- Excellent
- Good
- Fair
- Poor

During hospitalization only:

15. Based on the clinical status of the subject, is the subject ready to be discharged?

- Yes
- No

At the Day 7 visit only (only for studies in which study drug is administered):

16. In general, was the oral dosing of the study medication well tolerated by the subject?

- Yes
- No

17. Study drug administration

17.1 During study drug administration, were any of the following reported? (note all that apply)

- Disgusted expressions after tasting medicine
- Cried after tasting medicine
- Refused (would not open mouth or turned head away to avoid medicine)

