5. EFFICACY

All efficacy will be analyzed on the Intention-To-Treat-infected (ITT-i) set.

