5.4. Pediatric RSV Electronic Severity and Outcome Rating System (PRESORS)

5.4.1. Definition

Currently, no single outcome assessment tool is widely accepted to assess the severity of RSV in infants and children. Although various clinical scores have been developed for the evaluation of the severity of acute respiratory infections and/or bronchiolitis in infants and children, none have been sufficiently validated for the longitudinal monitoring of the severity of RSV infection. Considering that there are no widely accepted or fully validated clinical endpoints for use in studies of RSV treatment, the PRESORS, an electronic clinician and parent/caregiver RSV infection severity rating assessment, will be further developed and evaluated for validity and reliability in a phase 0 trials, 64041575RSV0001.

The PRESORS data may also be analyzed for specific psychometric properties outside the scope of this protocol (possibly in conjunction with data from study 64041575RSV0001). In that case results will also be reported separately.

This study includes the same version of the PRESORS as in this validation study. The scoring system that will be used during this validation is available in attachment 4.

The PRESORS scores are defined as in table below. These will be calculated at each scheduled time point a questionnaire was filled in. A change from baseline will also be calculated.

Domain	Items	Scoring
Severity of signs and symptoms during the past 12 hours as assessed by the Clinician	Attachment 4: Items 1-5 (Clinician)	Sum of the individual item scores. See appendix for item score.
Severity of signs and symptoms now as assessed by the Clinician	Attachment 4: Items 6-14 (Clinician)	Sum of the individual item score. See appendix for item score.
Study drug administration as assessed by the Clinician	Clinician's Items: Study drug administration	Number of reports, ranging from 0 (no reports) to 6.
Severity of signs and symptoms as assessed by the Caregiver	Attachment 4: Items 1-12 (Caregiver)	Sum of the individual item score. See appendix for item score.
Breaths/minute	Caregiver: Breaths/15s	4 times the Breaths per 15 seconds
Improvement during the past 12 hours as assessed by the Clinician	Attachment 4: Items 1-5 (Clinician)	Number of signs and symptoms that have decreased by at least 2 points during the past 12 hours as assessed by the Clinician per time point.

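### Children dosed only by nasogastric tube enter the palatability summaries, where four of the six reactions cannot meaningfully occur, so acceptance of the oral suspension is overstated

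*Protocol*

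**What the plan says.** Protocol Section 7 (Treatment Compliance) allows two routes in hospital: "Study drug will be administered orally or via nasogastric tube (if applicable) by designated study-site personnel". Protocol 2.1.2 lists as a secondary endpoint "Acceptability and palatability of the lumicitabine formulation as assessed by the parent(s)/caregiver(s) eCOA".

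Two sets of items in Protocol Attachment 5 collect the relevant data, both at Day 7.

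- **Clinician items 17.1 and 17.2** list three reactions each, such as "Disgusted expressions after tasting medicine" and "Cried after tasting medicine". Each item also has a box for no reaction reported.
- **Caregiver item 20** lists the same six kinds of reaction. Its only other option is that the child took the medicine easily.

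Neither form asks about route or offers a not-applicable answer. Clinician item 16 mentions oral dosing but accepts only yes or no.

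SAP 5.4.1 scores the clinician items as "Number of reports, ranging from 0 (no reports) to 6", and says of the PRESORS scores: "These will be calculated at each scheduled time point a questionnaire was filled in". Caregiver item 20 has no score and falls under the frequency tabulations of individual items in SAP 5.4.2, which include Day 7. These analyses sit in SAP Section 5, which opens: "All efficacy will be analyzed on the Intention-To-Treat-infected (ITT-i) set". No analysis set, subgroup (SAP 2.3, 2.4) or scoring rule refers to route.

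**The concern.** Palatability describes how children accept the suspension by mouth. A child who received every dose by tube gives no information on that, yet the forms leave the rater no neutral answer: with no reaction seen, the entry is the favourable one. Such children then sit in the denominator as acceptors.

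Tube dosing is foreseeable here. Protocol 9.2 evaluates nasogastric feeding as part of the clinical course and plans endotracheal sampling from intubated children, and exclusion criterion 6 removes only children whose gut cannot absorb. At stake is a reported secondary result that would describe the formulation as better accepted by mouth than it was.

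**Working it through.** **Step 1: the plan's own figure.** Items 17.1 and 17.2 list 3 reactions each, and 3 + 3 = 6, which matches the SAP's maximum of 6.

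**Step 2: which reactions a tube-only child can show.**

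| Reaction (clinician item) | Needs tasting or dosing by mouth? |
|---|---|
| Disgust after tasting (17.1) | Yes |
| Crying after tasting (17.1) | Yes |
| Refusing to open the mouth or turning away (17.1) | Yes |
| Spitting or coughing out (17.2) | Yes |
| Gagging (17.2) | No |
| Vomiting (17.2) | No in effect, though worded for swallowing |

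Four of six (67%) cannot meaningfully occur, so the attainable score for a tube-only child is 0 to 2. The same four of six apply to caregiver item 20.

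**Step 3: dilution of each of the four items.** Let f be the share of children dosed only by tube and r the frequency of the item among children with any oral dosing. The tabulated frequency is (1 − f) × r, so the relative shortfall is f whatever r is: 5%, 10%, 20% or 30% at those tube-only shares.

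**Step 4: dilution of the any-reaction rate.** Pooled rate = (1 − f) × p + f × q, where p is the rate among children with any oral dosing and q the rate of gagging or vomiting among tube-only children. The documents give none of f, p or q; the values below are assumptions chosen to show a range.

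| p | q | f = 5% | f = 10% | f = 20% | f = 30% |
|---|---|---|---|---|---|
| 30% | 0% | 28.5% | 27.0% | 24.0% | 21.0% |
| 50% | 0% | 47.5% | 45.0% | 40.0% | 35.0% |
| 70% | 0% | 66.5% | 63.0% | 56.0% | 49.0% |
| 30% | 20% | 29.5% | 29.0% | 28.0% | 27.0% |
| 50% | 20% | 48.5% | 47.0% | 44.0% | 41.0% |
| 70% | 20% | 67.5% | 65.0% | 60.0% | 55.0% |

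The understatement is f × (p − q). With q = 0 it runs from 0.05 × 30 = 1.5 to 0.30 × 70 = 21 percentage points. With q = 20% it runs from 0.05 × 10 = 0.5 to 0.30 × 50 = 15 points.

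**The case against.** The strongest objections, and what remains of each:

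- **The 0 to 6 count is not the endpoint.** It is clinician-rated, while the endpoint is caregiver-rated. SAP 5.4.2 summarises values for the severity scores, so a mean of this count may not be a planned output. This stands. The point therefore rests on the item frequencies, and caregiver item 20 has the same gap.
- **Many tube-dosed children will also taste the drug.** The tube is mentioned for dosing by site staff in hospital, discharge is possible after Day 2, and the Day 7 items ask about dosing overall. A reader might infer that any use of a tube caps the score at 2. The documents do not support that: a child who moves from tube to mouth can show any of the reactions. The cap holds only for tube-only children.
- **Route may be recorded.** A reader might infer that it is not, because the eCRF dosing items in Protocol Sections 6 and 9.1.3 are date, time and food. That list is not exhaustive: Section 7 adds vomiting and incomplete swallowing and requires an administration log, and neither the log nor the eCRF is before us. A missing route field cannot be established.
- **Proxies exist.** Supplemental feeding is collected and caregiver item 12 asks about tubes. But the SAP 5.3.1.3 feeding variable pools intravenous and nasogastric support, and item 12 excludes medicine, so neither identifies the route of study drug.
- **Arms are randomised and blinded, with placebo volumes matched.** A reader might infer a bias between arms or between dose volumes, since tube use after randomisation could respond to treatment. Nothing in the documents links arm or volume to tube use, so this remains speculation.
- **Tolerating tube dosing is arguably part of acceptability.** This is fair, and it argues for showing tube-only children separately rather than discarding them.

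**Conclusion.** The point holds for children dosed only by tube. Summarised as written, the Day 7 items count them as favourable responders and overstate acceptance of the oral suspension. That tube-only children are included is inferred from the absence of any route rule; no sentence says so.

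The direction is certain for the four items that need tasting or dosing by mouth. For the any-reaction rate it requires only that tube-only children report reactions less often than orally dosed children. The size cannot be fixed from the documents, because the tube-only share is not given; the ranges above are illustrative. The expected consequence is overstated acceptance overall, with no demonstrated bias between arms. The result is a descriptive secondary one, and the primary endpoint, alpha and sample size are unaffected.

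**What to change.** 1. Make sure that route (oral or nasogastric) is captured for each dose in the dosing log and eCRF. If a route field already exists, nothing is added.
2. In SAP 5.4.1 and 5.4.2, present clinician items 17.1 and 17.2 and caregiver item 20 by route group: oral only, mixed, tube only. Mixed-route children need their own row because the Day 7 answers cannot be attributed to one route.
3. Take the palatability result from children with oral dosing, excluding tube-only children.
4. Show the number of tube-only and mixed-route children by arm, so that any imbalance in this post-randomisation grouping is visible.

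The cost is at most one eCRF field and a short addition to the SAP. The downside is a smaller denominator for a descriptive endpoint: with 60 children planned per regimen, tube-only shares of 5%, 10%, 20% and 30% would leave 57, 54, 48 and 42. The change concerns data capture and analysis only and leaves dosing as it is.
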